4.5.14.5 Consent to Participate in the Research Biosample Repository

The Informed Consent Form will contain a separate section that addresses participation in the RBR. The investigator or authorized designee will explain to each patient the objectives, methods, and potential hazards of participation in the RBR. Patients will be told that they are free to refuse to participate and may withdraw their consent at any time and for any reason during the storage period. A separate, specific signature will be required to document a patient's agreement to provide optional RBR samples. Patients who decline to participate will not provide a separate signature.

The investigator should document whether or not the patient has given consent to participate and (if applicable) the date(s) of consent, by completing the RBR Research Sample Informed Consent eCRF.

In the event of an RBR participant's death or loss of competence, the participant's samples and data will continue to be used as part of the RBR research.

4.5.14.6 Withdrawal from the Research Biosample Repository

Patients who give consent to provide RBR samples have the right to withdraw their consent at any time for any reason. After withdrawal of consent, any remaining samples will be destroyed or will no longer be linked to the patient. However, if RBR samples have been tested prior to withdrawal of consent, results from those tests will remain as part of the overall research data. If a patient wishes to withdraw consent to the testing of his or her RBR samples during the study, the investigator must inform the Medical Monitor in writing of the patient's wishes through use of the appropriate RBR Subject Withdrawal Form and must enter the date of withdrawal on the RBR Research Sample Withdrawal of Informed Consent eCRF. If a patient wishes to withdraw consent to the testing of his or her RBR samples after closure of the site, the investigator must inform the Sponsor by emailing the study number and patient number to the following email address:

[contact]

A patient's withdrawal from this study does not, by itself, constitute withdrawal of consent for testing of RBR samples. Likewise, a patient's withdrawal of consent for testing of RBR samples does not constitute withdrawal from this study.

4.5.14.7 Monitoring and Oversight

Research Biosample Repository samples will be tracked in a manner consistent with Good Clinical Practice by a quality-controlled, auditable, and appropriately validated laboratory information management system, to ensure compliance with data confidentiality as well as adherence to authorized use of samples as specified in this protocol and in the Informed Consent Form. Sponsor monitors and auditors will have direct access to appropriate parts of records relating to patient participation in the RBR for the purposes of verifying the data provided to the Sponsor. The site will permit monitoring, audits, IRB/EC review, and health authority inspections by providing direct access to source data and documents related to the RBR samples.

4.6 TREATMENT, PATIENT, STUDY, AND SITE DISCONTINUATION

4.6.1 Study Treatment Discontinuation

Patients must permanently discontinue study treatment if they experience any of the following:

- Intolerable toxicity related to study treatment, including development of an immune-mediated adverse event determined by the investigator to be unacceptable given the individual patient's potential response to therapy and severity of the event
- Any medical condition that may jeopardize the patient's safety if he or she continues study treatment
- Investigator or Sponsor determination that treatment discontinuation is in the best interest of the patient
- Use of another non-protocol-specified anti-cancer therapy
- Pregnancy
- Loss of clinical benefit as determined by the investigator after an integrated assessment of radiographic and biochemical data, local biopsy results (if available), and clinical status (e.g., symptomatic deterioration such as pain secondary to disease) (see Section 3.1.2 for details)

The primary reason for study treatment discontinuation should be documented on the appropriate eCRF. Patients who discontinue study treatment prematurely will not be replaced.

Patients will return to the clinic for a treatment discontinuation/completion visit ≤ 30 days after the final dose of study treatment (see [Appendix 1](#)), regardless of whether they complete all 13 cycles or discontinue early. The visit at which response assessment shows progressive disease may be used as the treatment discontinuation/completion visit. Patients who discontinue study treatment for any

reason other than progressive disease or loss of clinical benefit will continue to undergo tumor response assessments and PRO assessments as outlined in the schedule of activities (see [Appendix 1](#)).

After treatment discontinuation/completion, patients will continue to be followed in the post-treatment period (refer to [Appendix 1](#) for the list of assessments). The first follow-up visit should be scheduled approximately 3 months after the discontinuation/completion visit. Information on well-being checks (e.g., survival follow-up) and new anti-cancer therapy will be collected by means of telephone calls, patient medical records, and/or clinic visits approximately every 3 months until death (unless the patient withdraws consent or the Sponsor terminates the study) (see [Appendix 1](#)). Information on subsequent anti-cancer therapies will include systemic therapies (e.g., chemotherapy, targeted therapy, hormonal therapy, CIT, surgery [e.g., resection of metastatic disease]), and radiation procedures (e.g., RT to a tumor lesion).

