Patients will undergo tumor assessments at screening and every 8 weeks (± 7 days) for 48 weeks following Day 1 of Cycle 1 regardless of treatment delays (see Section 4.5.6 and Appendix 1). After completion of the Week 48 tumor assessment, tumor assessment will be required every 12 weeks (± 7 days) regardless of treatment delays until confirmed, investigator-assessed radiographic disease progression (as defined by growth of existing lesions, new lesions, or recurrence of previously resolved lesions) per RECIST v1.1, withdrawal of consent, or study termination by the Sponsor, whichever occurs first. Patients who are treated beyond disease progression per RECIST v1.1 will undergo tumor assessments at the frequency described above. Patients who discontinue treatment for reasons other than radiographic disease progression per RECIST v1.1 (e.g., toxicity, symptomatic deterioration, completion of study treatment) will continue scheduled tumor assessments at the frequency described above until confirmed radiographic disease progression per RECIST v1.1, withdrawal of consent,

death, or study termination by the Sponsor, whichever occurs first. In the absence of radiographic disease progression confirmed by scan per RECIST v1.1, tumor assessments should continue regardless of whether a patient starts a new anti-cancer therapy.

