Patient-reported outcomes (EORTC QLQ-C30, EORTC QLQ-LC13, EORTC IL46, and EQ-5D-5L) will be collected on Day 1 of Cycle 1 (baseline) prior to administration of study drug, and at every other study treatment cycle prior to the administration of study drug (i.e., on Day 1 of Cycles 3, 5, 7, etc.) until radiographic disease progression per RECIST v1.1, and at the study treatment discontinuation/completion visit. Patients who discontinue study treatment for any reason other than radiographic disease progression per RECIST v1.1 (e.g., toxicity, symptomatic deterioration) will complete PROs at each tumor assessment visit until radiographic disease progression per RECIST v1.1, withdrawal of consent, death, or study termination by the Sponsor, whichever occurs first.

During the post-treatment follow-up, PROs will be completed 3 months (\pm 30 days) and 6 months (\pm 30 days) following radiographic disease progression per RECIST v1.1 (or loss of clinical benefit for patients who continue study treatment after disease progression per RECIST v1.1). The PROs at 3 and 6 months after disease progression or after treatment discontinuation/completion visit may be collected by telephone.

Patients whose native language is not available with the questionnaires are exempted from completing all PRO assessments.

The Sponsor will not derive adverse events reports from PRO data (see Section 5.3.5.13).

4.5.10.2 Description of Clinical Outcome Assessment Instruments EORTC QLQ-C30, EORTC QLQ-LC13 and EORTC IL46

The EORTC QLQ-C30 is a validated, reliable self-reported measure (Aaronson et al. 1993; Fitzsimmons et al. 1999) (see [Appendix 5](#)). It consists of 30 questions that assess five aspects of patient functioning (physical, emotional, role, cognitive, and social), three symptom scales (fatigue, nausea and vomiting, and pain), GHS and QoL, and six single items (dyspnea, insomnia, appetite loss, constipation, diarrhea, and financial difficulties) with a recall period of the previous week. Scale scores can be obtained for the multi-item scales. The functioning and symptoms items are scored on a 4-point scale that ranges from "not at all" to "very much," and the GHS and QoL items are scored on a 7-point scale that ranges from "very poor" to "excellent." The EORTC QLQ-C30 module takes approximately 15 minutes to complete.

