Assessments should be performed by the same evaluator if possible to ensure internal consistency across visits. Results must be reviewed by the investigator before dosing at the next cycle. Patients who discontinue treatment for reasons other than confirmed radiographic disease progression (as defined by growth of existing lesions, new lesions, or recurrence of previously resolved lesions) per RECIST v1.1 (e.g., toxicity, symptomatic deterioration) will continue scheduled tumor assessments at the frequency described above until radiographic disease progression per RECIST v1.1, withdrawal of consent, death, or study termination by Sponsor, whichever occurs first. In the absence of radiographic disease progression per RECIST v1.1, tumor assessments should continue regardless of whether a patient starts a new anti-cancer therapy. Scans will be sent to an IRF for central review.

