When no imaging/measurement is done at all at a particular timepoint, the patient is not evaluable at that timepoint. If measurements are made on only a subset of target lesions at a timepoint, usually the case is also considered not evaluable at that timepoint, unless a convincing argument can be made that the contribution of the individual missing lesions would not change the assigned timepoint response. This would be most likely to happen in the case of PD. For example, if a patient had a baseline sum of 50 mm with three measured lesions and during the study only two lesions were assessed, but those gave a sum of 80 mm, the patient will have achieved PD status, regardless of the contribution of the missing lesion.

SPECIAL NOTES ON RESPONSE ASSESSMENT

Patients with a global deterioration in health status requiring discontinuation of treatment without objective evidence of disease progression at that time should be reported as "symptomatic deterioration." Every effort should be made to document objective progression even after discontinuation of treatment. Symptomatic deterioration is not a descriptor of an objective response; it is a reason for stopping study therapy. The objective response status of such patients is to be determined by evaluation of target and non-target lesions as shown in [Table 1](#) and [Table 2](#).

For equivocal findings of progression (e.g., very small and uncertain new lesions; cystic changes or necrosis in existing lesions), treatment may continue until the next scheduled assessment. If at the next scheduled assessment, progression is confirmed, the date of progression should be the earlier date when progression was suspected.

REFERENCES

Appendix 5

European Organisation for Research and Treatment of Cancer Quality-of-Life Questionnaire Core 30 (EORTC QLQ-C30) and EORTC Item List 46 (EORTC IL46)

Do not reproduce or distribute. The Sponsor will provide sites with all instruments to be completed in this study.

EORTC QLQ-C30 (version 3)

We are interested in some things about you and your health. Please answer all of the questions yourself by circling the number that best applies to you. There are no "right" or "wrong" answers. The information that you provide will remain strictly confidential.

Please fill in your initials:

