### 4.2 **PRIMARY ENDPOINTS ANALYSIS**

#### 4.2.1 **Definition of Primary Endpoints**

The primary efficacy endpoints for this study are IRF-assessed PFS according to RECIST v1.1 in the PPAS and FAS. The corresponding estimands are defined in [Table 1](#).

The primary efficacy endpoint is IRF-assessed PFS after randomization, defined as the time between the date of randomization and the date of first documented disease progression as assessed by the IRF according to RECIST v1.1, or death, whichever occurs first. Patients who have not experienced disease progression or died at the time

of analysis will be censored at the time of the last tumor assessment. Patients with no post-baseline tumor assessment will be censored at the date of randomization.

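### Protocol Section 4.6.1 implies that scans and PROs may stop at loss of clinical benefit, contrary to Sections 3.1.1, 4.5.6 and 4.5.10.1, Appendix 1 and SAP Section 1.2

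*Protocol*

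**What the plan says.** Protocol Section 4.6.1 lists the reasons for permanent discontinuation. One is loss of clinical benefit, which the investigator judges from imaging, biochemistry, any biopsy and the patient's "clinical status (e.g., symptomatic deterioration such as pain secondary to disease". RECIST progression is not a condition. The section then provides that patients who stop for any "reason other than progressive disease or loss of clinical benefit will continue to undergo tumor response assessments and PRO assessments", with a pointer to Appendix 1.

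The other sections draw the line elsewhere. Protocol Section 3.1.1 states: "Patients who discontinue treatment for reasons other than radiographic disease progression per RECIST v1.1 (e.g., toxicity, symptomatic deterioration, completion of study treatment) will continue". What goes on is the planned imaging, up to confirmed radiographic progression, consent withdrawal, death or study termination. Section 4.5.6, Appendix 1 footnote y and SAP Section 1.2 carry the same rule. Appendix 1 footnote aa adds: "In the absence of radiographic disease progression per RECIST v1.1, tumor assessments should continue regardless of whether a patient starts a new anti-cancer therapy". Appendix 4, on symptomatic deterioration, says: "Every effort should be made to document objective progression even after discontinuation of treatment".

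For PROs, Section 3.1.1 excepts only radiographic progression. Section 4.5.10.1 says that patients stopping for other reasons ("e.g., toxicity, symptomatic deterioration) will complete PROs at each tumor assessment visit until radiographic disease progression").

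For the primary endpoint, SAP Section 4.2.1 specifies that patients without progression or death at the time "of analysis will be censored at the time of the last tumor assessment".

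**The concern.** The IRF can date a progression only from scans that were taken and submitted. If a site reads 4.6.1 as releasing it from further scans, the patients who drop out of imaging are those judged to be failing, so progression is likely to be near. In IRF-assessed PFS they would be censored at the last scan if alive at cutoff, or counted at death, later than the missed progression. Investigator-assessed PFS and time to death or distant metastasis are exposed in the same way, and time to confirmed deterioration loses PRO assessments.

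The judgement is made by investigators who know the arm, so the loss could differ between arms. The estimand takes a treatment-policy approach to early discontinuation, which relies on data collected after treatment stops.

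**Working it through.** **Step 1: the texts applied to one patient.** Take a patient who stops for symptomatic deterioration, has no RECIST progression and has not withdrawn consent.

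| Source | Scans continue? | PROs continue? |
|---|---|---|
| Protocol 4.6.1 | Not provided for | Not provided for |
| Protocol 3.1.1 | Yes, patient type named | Yes, only radiographic progression excepted |
| Protocol 4.5.6 | Yes, patient type named | – |
| Protocol 4.5.10.1 | – | Yes, patient type named |
| Appendix 1, footnotes y and aa | Yes | PRO footnote not readable in the public copy |
| SAP 1.2 | Yes, patient type named | – |

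The conflict is established for scans and for PROs. It cannot be checked against Appendix 1 for PROs.

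**Step 2: possible size.** The plan gives no usable figure: PFS events, alpha, target hazard ratio and the related assumptions are redacted. What follows is an illustration.

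Inputs from the documents: about 800 patients, 1:1; control median PFS 16.8 months (the durvalumab result cited in Protocol 1.2.2); scans every 8 weeks to Week 48, then every 12; censoring at the last scan; death as an event.

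Assumed: exponential times; true hazard ratio 1.0 or 0.75; 24 months of accrual plus 24 of follow-up; 85% of first events are progressions; median survival after progression 6 or 18 months; 0 to 10% of progressors stop scanning before RECIST progression. The simulation used 40,000 patients per arm, scaled to 800, with an unstratified Cox model.

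Hand check of the base case at hazard ratio 1.0: rate = ln 2 / 16.8 = 0.0413 per month. Averaged over follow-up of 24 to 48 months, the event probability is 1 − (e^(−0.990) − e^(−1.980)) / 0.990 = 1 − (0.3715 − 0.1380) / 0.990 = 0.764, or about 611 of 800. The simulation gives 600 to 603, slightly fewer because progression is dated at the next scan.

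The table shows the hazard ratio under early stopping minus that under continued scanning, in the same simulated data.

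| Median survival after progression | Stopping, control / experimental | Shift, true HR 1.0 | Shift, true HR 0.75 | Censored instead of progressed, per 800 (HR 1.0; 0.75) |
|---|---|---|---|---|
| 6 months | 5% / 5% | 0.000 | 0.000 | 3.1; 3.5 |
| 6 months | 10% / 10% | −0.001 | 0.000 | 7.2; 7.0 |
| 6 months | 10% / 5% | +0.014 | +0.009 | 5.3; 5.2 |
| 6 months | 10% / 0% | +0.026 | +0.017 | 3.8; 3.6 |
| 6 months | 5% / 10% | −0.012 | −0.009 | 5.6; 5.4 |
| 18 months | 5% / 5% | 0.000 | −0.002 | 11.6; 11.2 |
| 18 months | 10% / 10% | 0.000 | −0.002 | 22.9; 21.8 |
| 18 months | 10% / 5% | +0.027 | +0.017 | 17.0; 16.3 |
| 18 months | 10% / 0% | +0.051 | +0.039 | 10.9; 11.1 |
| 18 months | 5% / 10% | −0.023 | −0.019 | 15.8; 16.3 |

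**Step 3: reading the table.** Roughly 0.85 × 600 = 510 patients progress, so 10% stopping affects about 51. With 18-month survival about 23 of them end up censored; with 6-month survival about 7. The rest die before cutoff and become late events. The direction follows the arm that stops more often. For scale, with 600 events the standard error of the log hazard ratio is about 2/√600 = 0.082. The largest shift, ln(1.062/1.011) = 0.049, is about 0.6 of that.

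**The case against.** Four points can be made for the plan.

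- **4.6.1 never says that assessments end.** It says who continues, and it points to Appendix 1, whose tumor footnotes require scans after symptomatic deterioration. This stands: the cut-off is implied, and a site would have to prefer that implication to several explicit rules. It does not remove the conflict, because 4.6.1 defines who follows Appendix 1 and leaves out a group that Appendix 1 includes.
- **The phrase may mean only patients treated beyond progression.** The loss-of-benefit item refers to Section 3.1.2, which concerns treatment after RECIST progression. Such patients normally already have a PFS event, and Section 4.5.6 ends their scheduled scans when treatment stops. The reading is plausible but not compelled. 4.6.1 names loss of clinical benefit separately from progressive disease, and it lacks the limiter that Section 4.5.10.1 uses when it means that group.
- **Deaths still count.** Survival follow-up runs to death, so many missed progressions become late events. This stands and limits the effect, most of all if these patients die soon.
- **A sensitivity analysis may address missed scans.** Part of SAP Section 4.2.3 is redacted, and the SAP reference list includes a method for interval-censored data. The plan cannot be said to ignore the problem, but no analysis recovers a scan that was not taken.

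A reader might infer that the treatment-policy strategy is defeated. The documents do not support that: the estimand and the censoring rule are unchanged, and at most some data would be missing. A reader might also infer a seriously inflated type I error. That needs a large imbalance between arms, such as 15% against 5%, together with long survival after progression in patients described as failing. The documents give no basis for either.

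**Conclusion.** The contradiction is real for tumor assessments and for PROs, and it bears on follow-up for the primary endpoint. Informative censoring is a risk and not an established consequence. It requires sites to act on 4.6.1 over the other sections. It reaches only patients without earlier IRF progression, and those who die before cutoff still count as events.

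Under the stated assumptions, equal stopping moves the hazard ratio by no more than about 0.002, with about 3 to 23 of 800 patients censored instead of counted as progressed. Differences of 5 to 10 percentage points between arms move it by about 0.01 to 0.05, in either direction, with about 4 to 17 censored. The stopping rates, survival after progression, accrual and share of progressions are assumptions, and the trial's own event target, alpha and target effect are not public. This is an inconsistency worth correcting; the documents do not show that the primary analysis is compromised.

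**What to change.** Reconcile the sentence in Section 4.6.1 with Sections 3.1.1, 4.5.6 and 4.5.10.1, Appendix 1 and SAP Section 1.2, so that patients who discontinue without radiographic progression per RECIST v1.1 continue scheduled tumor and PRO assessments under the end points already set there. Check the Appendix 1 PRO footnote for the same wording. Tell sites promptly, since missed scans cannot be recovered.

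In the SAP, add a table by arm of patients censored for IRF-assessed PFS after stopping for loss of clinical benefit without IRF progression. The primary reason for discontinuation is already recorded on the eCRF, so this needs no new data.

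The cost is one sentence in the protocol, a site letter and one table. No visit or scan is added beyond what the other sections already require.

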4.6.2 Patient Discontinuation from the Study

Patients have the right to voluntarily withdraw from the study at any time for any reason. In addition, the investigator has the right to withdraw a patient from the study at any time.

Reasons for patient discontinuation from the study may include, but are not limited to, the following:

- Patient withdrawal of consent
- Study termination or site closure
- Loss to follow-up
- Patient non-compliance, defined as failure to comply with protocol requirements as determined by the investigator or Sponsor

Every effort should be made to obtain a reason for patient discontinuation from the study. The primary reason for discontinuation from the study should be documented on the appropriate eCRF. If a patient requests to be withdrawn from the study, this request must be documented in the source documents and signed by the investigator. Patients who withdraw from the study will not be replaced.

If a patient withdraws from the study, the study staff may use a public information source (e.g., county records) to obtain information about survival status.

